11.0 Treatment Evaluation

11.1 Complete hematologic response (CR)

Less than 5% blasts in a non-hypocellular marrow with a granulocyte count ≥ 1.0 , and a platelets count ≥ 100 with complete resolution of any extramedullary disease and absence of peripheral blood blasts. The patient is in sustained CR if they have previously achieved a CR and continue to meet the CR criteria (at least 28 days).

CR incomplete (CR_i) is called if patient meets all CR criteria except for residual neutropenia (ANC < $1 \times 10^9/L$) or thrombocytopenia (platelets < $100 \times 10^9/L$)

- 11.11 Complete cytogenetic remission (CCyR)
The absence of chromosome abnormalities (if present at diagnosis) on conventional cytogenetic study using G-banding (at least 10 metaphases present).
- 11.12 Complete molecular remission (CMR)
The achievement of negative PCR for FLT3 mutation (if done and if present at diagnosis).
- 11.13 MRD: Minimal Residual Disease
Positive PCR for FLT3 mutation or flow cytometry for FLT3 overexpression from peripheral blood or bone marrow.
- 11.2 Morphologic leukemia-free state (MLFS):
If bone marrow blasts <5%, absence of Auer rods blasts, absence of extramedullary disease without hematological recovery.
- 11.3 Partial response (PR)
The presence of trilineage hematopoiesis in the bone marrow with recovery of ANC and platelet count to above levels, but with 5-25% bone marrow blasts and $\geq 50\%$ decrease in bone marrow blast percentage from baseline.
- 11.4 No response (NR)
Failure to achieve a PR, MLFS, CRi, or CR.
- 11.5 Relapse:
Disease recurrence after achieving CR. Disease recurrence is defined by blast $\geq 5\%$ in the bone marrow, or recurrence of peripheral blood blasts or extramedullary involvement.
- 11.6 Treatment failure:
Resistant disease: Failure to achieve CR/CRi/PR/morphologic leukemia-free state by the end of 8 cycles of induction .

Note: These patients will be recorded as an objective status of NR to document depth of response but will be considered treatment failures at the time of analysis.

Death in aplasia: Death occurring ≥ 7 days following completion of treatment with aplastic/hypoplastic bone marrow (obtained within 7 days of death) with no evidence of persistent leukemia

Death from indeterminate cause: Death occurring during therapy or < 7 days following treatment completion, or ≥ 7 days following completion of treatment with no blast in the blood but no bone marrow examination available

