16.3 Analysis Plan

16.31 Primary Outcome Analyses:

16.311 Definition: The primary endpoint of this trial is the proportion of complete responses to therapy. A success is defined as a CR or CRi as the objective status. All patients meeting the eligibility criteria who have signed a consent form and have begun treatment will be evaluable for complete response.

16.312 Estimation: The proportion of successes will be estimated by the number of successes divided by the total number of evaluable patients. Exact binomial confidence intervals for the true success proportion will be calculated.

16.32 Secondary Outcome Analyses:

- 16.321 Overall survival time is defined as the time from registration to death due to any cause. The distribution of overall survival will be estimated using the method of Kaplan-Meier {Kaplan E, 1958 #831}. In addition, the overall survival rate at 1 year after registration will be reported.
- 16.322 Progression-free survival time is defined for all evaluable patients as the time from registration to the time of relapse or death due to any cause. The distribution of progression-free survival will be estimated using the method of Kaplan-Meier. In addition, the progression-free survival rate at 1 year after registration will be reported.
- 16.323 The overall response rate will be estimated by the total number of complete or partial responses (CR, CRi, MLFS, or PR) divided by the total number of evaluable patients. All evaluable patients will be used for this analysis. Exact binomial 95% confidence intervals for the true overall response rate will be calculated.
- 16.324 Duration of complete response is defined for all evaluable patients who have achieved a CR or CRi as the date at which the patient's objective status is first noted to be a CR or CRi to the earliest date relapse is documented. The distribution of duration of complete response will be estimated using the method of Kaplan-Meier. If there are a sufficient number of CR/CRi, a landmark analyses may be performed to compare duration of CR/CRi in patients who first achieved a CR/CRi at 2 months vs those who first achieved a CR/CRi at 8 months.

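### MLFS has no marrow-evaluability condition, so a marrow too empty to give a meaningful blast percentage counts in the overall response rate

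*Combined protocol and SAP*

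**What the plan says.** Section 11 sets out the response statuses.

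- **CR (11.1)** begins "Less than 5% blasts in a non-hypocellular marrow with a granulocyte count" and adds thresholds for counts.
- **CRi (11.1)** "is called if patient meets all CR criteria except for residual neutropenia" or thrombocytopenia. It waives counts only, so it keeps CR's marrow condition.
- **PR (11.3)** requires trilineage hematopoiesis and recovered counts.
- **MLFS (11.2)** reads "If bone marrow blasts <5%, absence of Auer rods blasts, absence of extramedullary disease without hematological recovery". Nothing is said about cellularity or the number of cells examined.
- **No response (11.4)** is "Failure to achieve a PR, MLFS, CRi, or CR", so a patient with MLFS cannot be a non-responder.

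Section 16.323 states: "The overall response rate will be estimated by the total number of complete or partial responses (CR, CRi, MLFS, or PR"), divided by all evaluable patients, with an exact 95% interval. Goal 2.22 makes this rate a secondary objective.

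Section 11.6 lists death in aplasia under treatment failure: "Death occurring ≥ 7 days following completion of treatment with aplastic/hypoplastic bone marrow (obtained within 7 days of death) with no evidence of persistent leukemia".

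MLFS is also one of the statuses used at the end of cycle 2 and of cycle 8 in 7.11, and at the end of cycle 8 in 13.1.

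**The concern.** A blast percentage is informative only if there are enough cells to count. Both study drugs can suppress the marrow: 15.29 describes myelosuppression as dose limiting for decitabine. In an aplastic or nearly empty marrow, blasts fall below 5% because cells of every kind are scarce, and blood counts have not recovered. Such a marrow meets every item in 11.2. It is barred from CR and CRi, cannot be PR, yet enters the overall response rate as MLFS.

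What is at stake is how a secondary efficacy estimate can be read. With 24 patients, one marrow scored this way visibly moves the reported rate, and nobody reading the result could tell a cleared marrow from an emptied one.

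**Working it through.** **1. The design figures, to see whether they are touched.** Inputs: n = 24, at least 5 successes, null 10%, alternative 30% (16.21, 16.211). P(X ≥ 5) = 1 − Σ C(24, x) pˣ (1 − p)²⁴⁻ˣ, summed over x = 0 to 4.

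| True rate | 0.10 | 0.15 | 0.20 | 0.25 | 0.30 |
|---|---|---|---|---|---|
| Recomputed | 0.0851 | 0.2866 | 0.5401 | 0.7534 | 0.8889 |
| Stated in 16.24 | 0.09 | 0.29 | 0.54 | 0.75 | 0.89 |

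The table reproduces to two decimals. A success is CR or CRi (16.11), and both need a non-hypocellular marrow, so an empty marrow cannot count toward the 5.

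**2. One record taken through the definitions.** Take a patient with an aplastic marrow, blasts under 5%, no Auer rods, no extramedullary disease, ANC below 1 and platelets below 100.

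| Rule | Result |
|---|---|
| CR, CRi (11.1) | No: marrow is hypocellular |
| PR (11.3) | No: no trilineage hematopoiesis, counts not recovered |
| MLFS (11.2) | Yes: every listed item is met |
| No response (11.4) | No: MLFS excludes it |
| Overall response (16.323) | Yes |

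Nothing later reverses this. Section 16.323 has no confirmation, duration or evaluability rule, and Section 11 has no not-assessable category. The protocol does set a minimum count where it wants one: 11.11 asks for at least 10 metaphases before calling a cytogenetic remission.

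**3. Direction and size.** The denominator in 16.323 is all evaluable patients and does not depend on the marrow reading. Scoring an empty marrow as MLFS can therefore only add to the numerator, and it matters only for a patient with no other qualifying marrow. The effect per patient is 1/24 = 4.2 points. If all 26 planned patients were evaluable and entered the estimate under 16.34, it would be 1/26 = 3.8 points.

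**4. Illustration with assumed counts.** The documents give neither an expected overall response rate nor an aplasia rate, so both inputs here are assumptions. Intervals are Clopper-Pearson 95%, with limits Beta(0.025; x, n − x + 1) and Beta(0.975; x + 1, n − x), n = 24.

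| Empty marrows scored as MLFS | Starting from 5 true responders | Starting from 7 true responders |
|---|---|---|
| 0 | 20.8% (7.1 to 42.2) | 29.2% (12.6 to 51.1) |
| 1 | 25.0% (9.8 to 46.7) | 33.3% (15.6 to 55.3) |
| 2 | 29.2% (12.6 to 51.1) | 37.5% (18.8 to 59.4) |
| 3 | 33.3% (15.6 to 55.3) | 41.7% (22.1 to 63.4) |

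**The case against.** **The missing cellularity condition may be deliberate.** CRi already takes a non-hypocellular marrow with under 5% blasts and unrecovered counts, provided there are no blood blasts and the neutropenia-or-thrombocytopenia wording is read inclusively. Cellularity is then the main thing separating MLFS from CRi. Barring every hypocellular marrow from MLFS would nearly empty the category and leave evaluable, blast-cleared hypocellular marrows with no response status. This objection stands. It rules out a blanket cellularity requirement, but it does not explain why a marrow with too few cells to count should be a response.

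**A reader might infer that 11.2 and 11.6 contradict each other,** with one marrow being both response and failure whenever the patient dies. The documents do not support that. Death in aplasia needs death at least 7 days after completing treatment and a marrow taken within 7 days of death. The scheduled on-treatment marrows fall at day 1 of cycles 3, 5 and 9, so usually only an end-of-treatment or unscheduled marrow could meet both. Death during therapy falls under indeterminate cause, which 11.6 also lists, but not because of the marrow. A patient may also respond and later die. Section 16 defines no treatment-failure rate; 16.25 only mentions patterns of failure, so no two reported estimates conflict. What remains is narrow: no rule says how a patient who meets both definitions counts in 16.323.

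**The problem may be rare.** Marrows are taken at the start of a cycle, which may be delayed for hematological reasons, so they are not timed to the nadir. This is fair, and it is why no expected size can be given. A hematopathologist might also decline to report an empty marrow as MLFS, but the written rule does not require that.

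**Conclusion.** The point holds for the overall response rate. Followed as written, 11.2 and 16.323 score a non-evaluable marrow as a response, and MLFS is the only response status exposed to this. The bias runs one way: up by 4.2 points per affected patient at n = 24. The number affected is unknown, and the counts of 1 to 3 above are assumptions.

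It goes no further than that. The primary endpoint, the decision rule, alpha (0.0851 exact) and power (0.8889 at 30%) do not move. The overall response rate has no threshold or hypothesis attached. A reader might also infer that the rule would favor a more myelotoxic regimen, but this is a single-arm trial and makes no such comparison. Deaths still count in OS and PFS however the marrow is labeled. The correction is worth making because the rate is a stated goal, the sample is small and the change is cheap.

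**What to change.** In 16.323:

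1. Count MLFS toward the overall response rate only when the marrow is evaluable, meaning it meets a minimum number of counted cells or a minimum cellularity set by the study hematologist. Say explicitly that hypocellular marrows meeting that floor still qualify.
2. Keep a patient whose only qualifying marrow is non-evaluable in the denominator as a non-responder.
3. State that a patient is not a responder solely on the aplastic marrow that defines death in aplasia in 11.6.
4. Report MLFS as a separate line within the overall response rate.

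This needs no extra marrow and no change in sample size, because marrow reports are already collected under 18.1. The cost is wording, one threshold to agree, and possibly a slightly lower reported rate.

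Placing the floor in 16.323 leaves 11.2 itself unchanged. That matters because 7.11 and 13.1 use MLFS in treatment decisions. The sponsor should reconcile those passages, and the boundary between MLFS and CRi in 11.1 and 11.2, with the clarified definition. No clinical rule is proposed here.

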12.0 Descriptive Factors

- 12.1 FLT3 mutation at baseline: ITD vs. TKD vs. both
- 12.2 Bone marrow transplant candidate: Yes vs. No.
- 12.3 NPM1(Mutation): Positive vs. Negative vs. Not Done

13.0 Treatment/Follow-up Decision at Evaluation of Patient

13.1 Criteria for Patient Initiation of Event Monitoring:

- Delay > 28 days for the next cycle (due to non-hematological drug toxicity)
- Disease relapse
- Failure to achieve CR or CRi or PR or MLFS by end of cycle 8
- Patient withdraws consent to continue in the trial
- Patient develops an intercurrent illness that precludes further participation
- The Investigator withdraws the patient in the patient's best interests
- Administrative reasons (e.g., the patient is transferred to hospice care)
- An adverse event, which in the opinion of the Investigator precludes further trial participation
- Patient discontinues either the Decitabine or the Midostaurin in the maximum 18 cycles.

All attempts should be made to complete the End of Study procedures if a patient withdraws from the trial early. The patient will go to the event-monitoring phase per Section 18.0.

- 13.2 Patients who achieve and sustain a CR/CRi/PR/MLFS by end of cycle 8, will receive a maximum total of 18 cycles of treatment. After 18 cycles, the patient will go to event monitoring, unless they are continuing the combination of midostaurin and decitabine beyond 18 cycles per section 7.12.
- 13.3 Event monitoring: Patients who are alive will be followed in event monitoring every 6 months until death or up to 2 years from registration.
- 13.4 A patient is deemed *ineligible* if after registration, it is determined that at the time of registration, the patient did not satisfy each and every eligibility criteria for study entry. The patient may continue treatment off-protocol at the discretion of the physician as long as there are no safety concerns, and the patient was properly registered. The patient will go directly to the event-monitoring phase of the study (or off study, if applicable).
 - If the patient received treatment, all data up until the point of confirmation of ineligibility must be submitted. Event monitoring will be required per Section 18.0 of the protocol.
 - If the patient never received treatment, on-study material and the End of Active Treatment/Cancel Notification Form must be submitted. No further data submission is necessary.

- 13.5 A patient is deemed a *major violation*, if protocol requirements regarding treatment in cycle 1 of the initial therapy are severely violated that evaluability for primary end point is questionable. All data up until the point of confirmation of a major violation must be submitted. The patient will go directly to the event-monitoring phase of the study. The patient may continue treatment off-protocol at the discretion of the physician as long as there are no safety concerns, and the patient was properly registered. Event monitoring will be required per Section 18.0 of the protocol.
- 13.6 A patient is deemed a *cancel* if he/she is removed from the study for any reason before any study treatment is given. On-study material and the End of Active Treatment/Cancel Notification Form must be submitted. No further data submission is necessary.

14.0 Body Fluid Biospecimens

14.1 Summary Table of Research Blood and Body Fluid Specimens to be collected for this Protocol

	Mandatory (M) or Optional (O)	Blood or Body Fluid being Collected	Type of Collection Tube (color of tube top)	Volume to collect per tube (# of tubes to be collected)	Screening	Cycle 1 Day 8 (pre-midostaurin treatment, 30 mins pre-dosing)	Day 1 Cycles 3, 5, and 9	Temperature Conditions for Storage /Shipping
Correlative studies - See sect. 14.21	M	Blood	BD Vacutainer EDTA 10ml 366643	30-40 ml in total(10 ml tubes)	yes	yes	No	Ship right away away (ice bags +4C) or pick up, room temperature
Correlative studies - See sect. 14.21	M	Bone marrow aspirate ¹	BD Vacutainer EDTA 10ml 366643	20-30 ml in total(4 ml tubes)	yes	no	yes	Ship right away away (ice bags +4C) or pick up, room temperature

1. If bone marrow done previously , this may be omitted.

When possible, samples should be obtained prior to the midostaurin dose. The exact time since the last dose of midostaurin should be documented. For the correlative studies, blood samples should be collected at screening, cycle 1 day 8. For the correlative studies, bone marrow aspirate samples should be collected at screening, and day 1 of cycle 3, 5, 9.

14.2 Collection and Processing

14.21 Genetic Targets Correlative studies: Compare the pre-treatment with post-treatment samples for the alterations of direct and potential-indirect targets for both midostaurin and decitabine:

1) FLT3 gene mutation status will be assessed (at Mayo Clinic Labs) for response stratification and MRD assessment by DNA sequencing;

2) Measurement of FLT3 kinase activities by PCR and Western blot, including FLT3 phosphorylation, total protein expression and downstream effectors (e.g. AKT, ERK, STAT5);

3) Determination of DNMT activity, including DNMT RNA and protein expression (by PCR and Western blot), expression of methylation-silenced tumor suppressor genes (by PCR), global DNA methylation (by LINE-1 or dotblot), gene promoter methylation analysis (by bisulfite sequencing);

4) Detection of microRNAs expression (by qPCR), because previous report show that *miR29b* functions as DNA methylation modulator (Garzon and Liu *et al*, 2009), regulates the activity of c-KIT (Liu *et al*, 2010), a FLT3-like receptor tyrosine kinase and predicts the outcome of decitabine therapy (Blum W *et al*, 2010).

5) Determination of indirect and potential targets, including the genes controlling histone modifications and RNA methylation by qPCR, Western blot, Dotblot and bisulfite sequencing.

6) Investigate the synergistic effect (using the methods above) of decitabine combined with PKC412 on the activities of DNA methylation and kinases, including their gene expression, alteration of downstream effectors and ultimately the synergetic clinical outcomes.

7) Gene and microRNA profiling. In order to further understand the molecular mechanism of drug effects, gene and miR microarrays will be performed in the group of a) responder versus non-responder; b) pre-treatment versus post-treatment. These experiments will identify innovative therapeutic targets.

8) Determination of growth factors, ligands and cytokines in plasma. It is increasingly recognized that leukemia are caused by the cooperation of multiple gene networks, not just a single pathway. Our preliminary data showed that there exists a crosstalk/interplay between methylation and kinases as well as the relevant cytokines, growth factors and lipid binding proteins. To precisely understand the molecular mechanisms underlying the anti-leukemia effects of midostaurin and decitabine, it is necessary to carry out the Western blot or/and ELISA to assess the changes of these gene networks pre- versus post- treatment.

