The FMS-like tyrosine kinase 3 (FLT3) belongs to the group of class III receptor tyrosine kinases. It belongs to a family of important signaling receptors that include c-KIT, c-FMS, and PDGFR. FLT3 is a growth factor receptor involved in hematopoietic cell growth and differentiation. FLT3 receptor and its ligand (FL) also play an important role in survival and self-renewal of early hematopoietic progenitors, monocytic precursors and in lymphoid development. Activation of FLT3 results in receptor auto-phosphorylation leading to downstream signaling of the RAS/MAPK, JAK/STAT5, and PI3K/AKT pathways. In normal bone marrow (BM), FLT3 is expressed on progenitor cells and regulates stem cell proliferation. As hematopoietic progenitor cells differentiate and mature, FLT3 expression is normally lost.

In AML, signaling of FLT3 pathway is often activated and leads to malignant blast cell proliferation, in part due to over expression of FLT3 receptor in leukemia cells. However, a major research advance was the identification of mutations occurring in the FLT3 gene in AML patients. It is the most common somatic mutation identified in AML, with an incidence of about 25% ([Kindler 2010](#), [Kottaridis 2001](#)). Two major types of FLT3 gene mutation have been identified: 1) internal tandem duplication (ITD) and 2) tyrosine kinase domain (TKD) point mutations (PM) and ITDs make up a majority of FLT3 mutations in newly diagnosed patients ([Thiede 2002](#)). These duplications are the result of 3 to > 400 base pairs inserted into the receptor in-frame ([Schnittger 2002](#)). The ITDs promote ligand-independent FLT3 receptor dimerization and signal activation, culminating in cellular proliferation ([Kiyoi 1998](#), [Hayakawa 2000](#)).

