14.33 Handling Specimens

After receipt by the analytical laboratory, samples will be stored at -20 °C or less until analysis.

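### Pre/post comparison of marrow targets makes no stated allowance for blast percentage, so total FLT3 and similar blast-enriched markers will tend to fall in responders without any per-cell drug effect

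*Combined protocol and SAP*

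**What the plan says.** **Comparison.** Section 14.21 sets out to "Compare the pre-treatment with post-treatment samples for the alterations of direct and potential-indirect targets for both midostaurin and decitabine". Item 2 is "Measurement of FLT3 kinase activities by PCR and Western blot, including FLT3 phosphorylation, total protein expression and downstream effectors". Other items cover DNMT, methylation, microRNA and histone-related genes. Item 7 adds gene and microRNA arrays for "a) responder versus non-responder; b) pre-treatment versus post-treatment. These experiments will identify innovative therapeutic targets", with the molecular mechanism of drug effects as the stated aim.

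**Specimens.** Under section 14.1, "blood samples should be collected at screening, cycle 1 day 8", the second before midostaurin is given, while "bone marrow aspirate samples should be collected at screening, and day 1 of cycle 3, 5, 9". Marrow is thus the only research specimen scheduled after midostaurin starts.

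**Handling.** Sections 14.1 to 14.33 cover collection and shipping; then "After receipt by the analytical laboratory, samples will be stored at" a freezing temperature. They mention no cell separation, blast enrichment or minimum blast percentage.

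**Analysis.** Section 16.33 covers prognostic factors and MRD. It gives no method for the 14.21 comparisons.

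**Biology and response.** Section 1.1 describes FLT3 over-expression in leukemia cells and adds: "As hematopoietic progenitor cells differentiate and mature, FLT3 expression is normally lost". Section 11.1 requires "Less than 5% blasts in a non-hypocellular marrow" for CR, and CRi keeps that blast criterion. MLFS (11.2) also needs under 5% blasts. PR (11.3) needs 5-25% with at least a halving from baseline.

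**The concern.** A bulk assay on unselected marrow measures the mixture of cells in the tube. Response is defined by a change in that mixture, and the protocol itself says FLT3 belongs mainly to the cells that disappear. A fall in total FLT3 after treatment can therefore mean less FLT3 per leukemic cell, fewer leukemic cells, or both. The comparison as described cannot tell these apart.

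This goes beyond missing laboratory detail because the results are meant to inform drug mechanism, and item 6 of 14.21 extends this to synergy between the two drugs. Any midostaurin effect on a cellular target has to come from the marrow series, which is where cell mix changes with response. At stake is whether goal 2.32 reports response itself as target modulation.

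**Working it through.** **Plan's own figure.** There is none. The documents give no sample size, effect size or test for these comparisons.

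**Step 1: apparent change with no drug effect per cell.** Let b be the marrow blast fraction and R the per-cell signal of a blast relative to a normal marrow cell. Bulk signal = bR + (1 - b). R is held constant, so the true per-cell change is zero.

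Inputs from the documents: 5% blasts as the boundary for CR/CRi (11.1), and 25% as the upper limit for PR (11.3). Assumptions: baseline blasts of 20%, 50% or 90%, and R of 2, 5 or 10.

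Example, baseline 50% and R = 5: before, 0.50 x 5 + 0.50 = 3.00; after, 0.05 x 5 + 0.95 = 1.20; change = 1.20/3.00 - 1 = -60%.

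| Blasts before to after | R = 2 | R = 5 | R = 10 |
|---|---|---|---|
| 20% to 5% | -12.5% | -33% | -48% |
| 50% to 5% | -30% | -60% | -74% |
| 90% to 5% | -45% | -74% | -84% |
| 50% to 25% (PR) | -17% | -33% | -41% |
| 50% to 50% (no response) | 0% | 0% | 0% |

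The artefact follows response. With R = 1 it vanishes.

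**Step 2: how often a test would reject.** This needs more assumptions, none from the documents: paired Wilcoxon test at 0.05, baseline blasts 20-90%, responders at 0.5-5%, non-responders varying around baseline, log-scale noise SD 0.3, and normal cells expressing 10-50% of the blast level.

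| Responder share | Pairs | False rejection |
|---|---|---|
| 30% | 12-24 | about 0.11 to 0.64 |
| 20% | 12-24 | about 0.07 to 0.35 |
| 10% (one or two responders) | 6-24 | about 0.03 to 0.1 |
| 10-30% (one or two responders) | 6-8 | about 0.03 to 0.1 |

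If normal cells express the marker as strongly as blasts, the rate is about 0.05. Upper limits move by several hundredths with the assumed variation in non-responders. They also rise somewhat if the number of responders is left to chance instead of fixed.

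For scale, section 16.21 uses success rates of 10% and 30%. In 24 patients that is 24 x 0.10 = 2.4 and 24 x 0.30 = 7.2 expected responders.

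**Step 3: does adjustment help?** Regressing the log change on the change in blast fraction and testing the intercept brings the rate to about 0.05-0.07 when normal cells express 30-50% of the blast level. At 10% it leaves about 0.06 to 0.24, depending on the other assumptions.

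**The case against.** The strongest reply is that the plan commits to nothing wrong. Whole marrow is inferred from silence, and the protocol does not list all bench work: item 8 of 14.21 measures plasma, yet no separation step is written. An external laboratory does the assays and might select blasts. No test is specified, so the paired Wilcoxon and its error rates belong to this review. Goal 2.32 is only exploratory.

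Much of this stands, and it rules out several stronger readings a reader might infer:

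- **That a false target finding is close to certain.** Such rates need a majority of responders, for example 60%. The documents cite 15-24% for decitabine alone and design around 10% and 30%. Pairs may also be few: 14.1 lets the research marrow be omitted if one was done previously, and 7.11 waives routine repeat marrow after CR/CRi.
- **That DNMT, methylation and microRNA results are equally distorted.** The documents tie only FLT3 to leukemic and immature cells. For the others, blast dependence is an assumption.
- **That every 14.21 item is affected.** Mutation and MRD status (item 1) is meant to follow leukemic burden, and plasma assays (item 8) do not measure cell content. Neither is affected in the same way.
- **That the responder versus non-responder arrays are confounded by blast loss.** This holds only if post-treatment samples are used, which item 7 does not say.

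What does not stand is that silence makes the point harmless. A bulk pre/post comparison read as drug mechanism is written into the protocol, and no safeguard is cited.

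**Conclusion.** The point holds for total FLT3 and any other marker enriched in blasts, measured in marrow that has not been blast-selected. With no per-cell effect, the apparent fall at 5% residual blasts is about 12-84%, given assumed baseline blasts of 20-90% and R of 2-10. In a non-responder with stable blasts it is zero. The direction follows from the protocol's account of FLT3 and its definition of CR; the size rests on those assumptions. False-positive rates depend on responder share, number of pairs and normal-cell expression, and are near nominal when responders or pairs are few.

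A reader might infer that the trial's efficacy conclusion is in doubt. It is not: the CR/CRi endpoint, its decision rule, the secondary endpoints and the safety rules do not use these measurements.

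**What to change.** In 14.21 and 16.33, for goal 2.32 only:

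1. State whether the laboratory selects blasts. If not, state that pre/post comparisons of cellular marrow markers are reported with, and adjusted for, the marrow blast percentage at the same time point. Sections 11.1-11.3 already need that percentage for response, and PR needs it at baseline too.
2. Report phospho-FLT3 relative to total FLT3, alongside blast percentage.
3. Make the responder versus non-responder profiling comparison on the screening sample.
4. Do not describe unadjusted pre/post changes as target effects.

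The cost is protocol wording, modest analysis work and one degree of freedom; no new sample is needed. Blast percentage must be matched to the research aliquot's time point, because section 18.1 does not link the marrow report to the research tube.

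Two limits should be stated. Adjustment stays imperfect in marrows with almost no blasts, or when normal cells express little of the marker. The phospho/total ratio is not immune either. If only blasts carry phosphorylated FLT3, at a constant fraction p, the ratio is p x bR/(bR + 1 - b). With R = 10 and blasts going from 50% to 5%, it moves from p x 5/5.5 = 0.91p to p x 0.5/1.45 = 0.34p with no drug effect. It is unaffected if the phosphorylated fraction is the same in both cell types, and nearly so if normal cells carry almost no FLT3.
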